In the clinical setting, lateral thoracic and lumbar spinal radiographs are the standard procedure for the diagnosis and assessment of vertebral fractures. Several qualitative and quantitative approaches have been developed to adjudicate a vertebral fracture, including a widely accepted Genant's semi-quantitative technique [21, 22]. However, in contrast to other fractures, most vertebral fractures receive little clinical attention and remain undiagnosed at the time of occurrence or during the lifetime [6, 9, 13]. The reason may be that most (up to 75%) vertebral fractures are absent from clinical signs and symptoms [22], and even only one fourth to one third of incident radiographically identified vertebral fractures are clinically diagnosed [23, 24]. As indicated in a previous report in 2011, there were an estimated 9 million new osteoporotic fractures worldwide in a particular year, among which only 1.4 million were clinical vertebral fractures and thus were medically cared [25]. Nevertheless, vertebral fractures are proven a strong predictor of a future fracture risk, at any skeletal site, which is independent of BMD [13, 26]. Women who have 2 or more vertebral fractures may have a 7-fold risk in having another vertebral fracture within one year, a 2 to 3-fold risk in having a future non-vertebral fracture, and a 2-fold risk in having a hip fracture, respectively [27]. Based on therapeutic guidelines [1, 2], a vertebral fracture is consistent with a diagnosis of osteoporosis (BMD DXA T-score ≤ 2.5) [1, 2] in the absence of a bone density diagnosis by dual-energy X-ray absorptiometry (DXA, DEXA). An early diagnosis of vertebral fractures is indicated for subsequent pharmacological therapy for osteoporosis, which is critical to prevent an add-on osteoporotic fracture.

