2.3 Exploratory Objective(s)

1. To assess the diagnostic accuracy of onsite radiology imaging for vertebral fractures in China's local clinical practice;
2. To assess the diagnostic role of vertebral imaging for the screening of osteoporosis and pharmacological treatment in China's local clinical practice.

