In the study, vertebral fracture is defined as the presence of at least one vertebra morphometrically classified as grade 1, 2, or 3 on Genant's score as agreed by the both radiographic assessments in the study. Two (2) experienced radiologists who are blinded to the study will separately review the vertebral morphology and grade Genant's Score as per protocol. Radiologists will receive additional training to reduce variability between inter-observer interpretations. Prior to the study, each site will forward sample radiographs to the radiology coordination site for quality assessment and to check compliance with the protocol and technical standard. Intra- and inter-observer reliabilities will be tested using first 100 X-ray images from any study site before the adjudication starts. If there is a disagreement in terms of Genant's grading between two study radiologists, a third party radiological review will give a final decision.

The Genant semi-quantitative approach has been established a reliable and reproducible assessment in radiographic vertebral fracture. The intra-observer agreement for prevalent vertebral fracture was generally between 93 and 97% ($\kappa = 0.73 - 0.89$) [51], regardless of the radiologist's experience. As compared with reviewer's experience and other quantitative methods, an inter-observer agreement by difference in experience and method was between 92 and 94% ($\kappa = 0.65 - 0.74$) [51].

Definitions of Osteoporosis

In the study, osteoporosis is defined [3, 41] if the subject has at least one of the following as:

- A BMD T-score ≤ -2.5 in at least one of the anatomic sites including the lumbar spine, the femoral neck, and the total hip;
- A proven prior non-pathological fragility fracture.

A fragility fracture is defined as a fracture that occurred with minimal trauma at a typical site of osteoporotic fracture that would be unlikely to cause fracture in a non-osteoporotic adult. This assessment will be made based on self-reported fracture section included in the questionnaire and a review of medical history/documents/physical examination, or as suggested by the radiographic imaging in the study.

5 Study Flow Chart

Study Period:	Enrollment		Observation	Follow-Up
Visit Number/ Title:	Invitation#	Screening [△]	Study Visit**	Unscheduled Visit***
Study Day	NA	1	1	NA
Informed Consent		X		
Medical History [※]		X		
Inclusion/Exclusion Criteria		X		
Investigator-administered Questionnaire [¶]		X	X	
Physical Examination*				

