8.1.2.1 Prevalence of Osteoporosis

In the study, prevalence of osteoporosis in community-dwelling postmenopausal women in China will be investigated as a secondary objective. Descriptive statistics will be made to statistically address this objective. Point estimates (percentage) and corresponding 95% CI (exact binomial and Wilson score) will be presented for each analysis category and will be adjusted by age distribution in China [53]. Prevalence rates will also be given by age group and geographic region. A case with osteoporosis is counted based on the definition in Section 4.

The prevalence of osteoporosis will be presented as overall and by different diagnostic criteria and will be listed separately to allow an evaluation on the frequency distribution of each individual diagnostic setting in the study population.

The analysis of osteoporosis prevalence is displayed in the Table 8.1.2.1.

Table 8.1.2.1 Statistical Analysis Approaches on the Prevalence of Osteoporosis

Osteoporosis	Rate*	Estimate**	Frequency ***
Overall	Crude/Age-Standardized	Point and 95% CI	Percent
By DXA BMD [^]	Crude/Age-Standardized	Point and 95% CI	Percent
By Fragility Fracture [△]	Crude/Age-Standardized	Point and 95% CI	Percent & Cumulative

* Prevalence rates will be sub-analyzed by age group (50 – 54, 55 – 59, 60 – 65, 65 – 69, 70 – 74, 75 – 79, and 80+; and by < 65 and ≥ 65) and/or geographic region (North, South, Southeast, Southwest, and Central);
 ** Based on exact binomial distribution 95% CI and Wilson Score 95% CI;
 *** Calculation of frequency is relative to overall percent (100%);
 ^ the subject with a T-score ≤ -2.5 as suggested by a DXA measurement
 △ The subject with DXA measurement with a proven non-pathological major fracture as reported by the medical history or as suggested by radiology.

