The diagnostic accuracy of onsite vertebral imaging will be tabulated by a simple 2*2 contingency table against blinded adjudication. Sensitivity, specificity, positive predictive value (PPV), negative predictive value (NPV), and likelihood ratio will be given with a corresponding 95% CI. Kappa test for inter-observer agreement between onsite and blinded experienced radiologists will be calculated and presented. Logistic regression model will also be used to assess the probability of a subject with adjudicated vertebral fracture will have the vertebral fracture as diagnosed onsite. The area under the Receiver Operating Characteristic (ROC) curve will be given to evaluate the degree of discrimination for the probability of interested response. Effects of age, region, and/or other analysis variables will be adjusted in the model whenever statistically appropriate.

Assessment in the diagnostic role of vertebral imaging for the screening of osteoporosis will be explored by a simple binary diagnostic test. An osteoporosis diagnosis in the study will be deemed as 'true condition' whereas the blinded vertebral imaging outcome will be the diagnostic tool. Sensitivity, specificity, PPV, NPV, and likelihood ratio will be presented with a corresponding 95% CI. Similarly, logistic regression model will also be used to assess the probability of a subject with adjudicated vertebral fracture will have densitometric osteoporosis. The area under the ROC curve will be given to evaluate the degree of discrimination for the probability of interested response. Effects of age, region, and/or other analysis variables will be adjusted in the model whenever statistically appropriate.

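### The exploratory 2x2 screening table scores vertebral imaging against an osteoporosis diagnosis that the study's own imaging can partly establish

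*Combined protocol and SAP*

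**What the plan says.** Section 2.3 sets an exploratory objective: "To assess the diagnostic role of vertebral imaging for the screening of osteoporosis and pharmacological treatment" in local practice. Section 8.1.3 answers it with a binary diagnostic table. "An osteoporosis diagnosis in the study will be deemed as" the true condition, "whereas the blinded vertebral imaging outcome will be the diagnostic tool". Sensitivity, specificity, PPV, NPV and likelihood ratio follow, each with a 95% CI.

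Section 4 (Definitions of Osteoporosis) gives two routes to the diagnosis, either of which suffices. One is a T-score of -2.5 or lower "in at least one of the anatomic sites including the lumbar spine, the femoral neck, and the total hip". The other is a proven prior non-pathological fragility fracture, judged from self-report, documents and examination, "or as suggested by the radiographic imaging in the study". Section 8.1.2.1 counts cases by the section 4 definition, and the footnote to Table 8.1.2.1 again admits fractures "as reported by the medical history or as suggested by radiology".

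The logistic/ROC step in the same paragraph of 8.1.3 uses another outcome. It is to "assess the probability of a subject with adjudicated vertebral fracture will have densitometric osteoporosis".

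**The concern.** A diagnostic test should be judged against a reference that does not use the test result. Here a woman with normal or osteopenic BMD and a vertebral fracture on the study film can become a true positive because the film is positive. Nothing in 8.1.3 takes imaging-detected fractures out of the reference or limits it to DXA.

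At stake is the planned answer to the second exploratory objective. A reader would use the PPV and LR+ to judge how well a spine film identifies osteoporosis, and part of what those figures show would be the definition agreeing with itself. Confidence intervals would not reveal this, because they describe sampling error only. The paragraph also answers one question with two reference standards and does not say why.

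**Working it through.** The plan states no accuracy figure to reproduce, so the check is structural, followed by an illustration of size.

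**Tracing the definition.** 8.1.3 takes the study's osteoporosis diagnosis as reference; 8.1.2.1 counts that diagnosis by section 4; section 4 accepts fractures shown by study radiographs. The overlap is partial: the fracture must be non-pathological and follow minimal trauma, and section 4 does not say whether the onsite or the blinded read counts.

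**Inputs.**
- Vertebral fracture (VF) prevalence: the weighted mean of Table 8.3.1, (44×5% + 81×7% + 100×12% + 90×16% + 80×20% + 70×23% + 53×37%)/518 = 85.98/518 = 16.6%. As a check on the table, 518/0.95 = 545.3 agrees with the stated 545 per region.
- DXA osteoporosis: 27.3%. Section 1.1 gives this figure for osteoporosis generally, so its use for DXA is an assumption.
- VF–DXA odds ratio: 2 (assumption).
- q, the share of DXA-negative imaging fractures accepted as fragility fractures: in no document, so varied from 0 to 1.
- r, the share of all women who qualify only by another fracture: 0 at first. When positive, it is placed among imaging-negative women.

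**Cells.** With fixed margins, solve a(1 − 0.166 − 0.273 + a) = 2(0.166 − a)(0.273 − a). This gives VF and DXA+ a = 0.066, VF and DXA− b = 0.100, no VF and DXA+ 0.207, neither 0.627. Check: 0.066×0.627 = 0.0414 and 2×0.100×0.207 = 0.0414.

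**Formulas.** Composite = 0.273 + bq + r; TP = a + bq; FP = 0.166 − TP; PPV = TP/0.166; sensitivity = TP/composite; specificity = 1 − FP/(1 − composite); NPV = (1 − composite − FP)/0.834; LR+ = sensitivity/(1 − specificity).

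Results for r = 0 (q = 0 is the DXA-only reference):

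| q | PPV | Specificity | Sensitivity | LR+ |
|---|---|---|---|---|
| 0 | 39.8% | 86.2% | 24.2% | 1.8 |
| 0.10 | 45.8% | 87.5% | 26.9% | 2.1 |
| 0.25 | 54.8% | 89.3% | 30.5% | 2.9 |
| 0.50 | 69.9% | 92.6% | 35.9% | 4.9 |
| 0.75 | 84.9% | 96.2% | 40.5% | 10.6 |
| 1 | 100% | 100% | 44.5% | infinite |

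NPV is 75.2% in every row.

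**Against sampling error.** 2700 less 5% is 2565 films, and 2565×0.166 is about 426 fracture cases. Exact 95% intervals for PPV, ignoring clustering, are 35–44% for 169/426 (DXA) and 65–74% for 298/426 (q = 0.50). The 30-point shift is about six times the interval half-width.

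**Other assumptions.** Over odds ratios 1.5–3 and DXA prevalence 20–35%, LR+ is 1.4–2.5 against DXA and 3.8–6.5 at q = 0.50. With no association (odds ratio 1, a = 0.045, b = 0.121) and r = 0, LR+ is 1.0 against DXA but 1.9, 3.5 and 7.9 at q = 0.25, 0.50 and 0.75.

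**Fractures proven without imaging.** These work the other way. At odds ratio 2 and r = 0.10:
- With q = 0.50, LR+ is 3.2, sensitivity 27% and NPV 63%.
- With q = 0.25, sensitivity is 0.091/0.398 = 22.9%, below the 24.2% against DXA.
- With q = 0, sensitivity is 0.066/0.373 = 17.7%. So at fixed r, accepting imaging fractures still raises it.

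At odds ratio 1, r = 0.10 and q = 0.10, LR+ is 0.84.

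**The case against.** Four objections carry weight.

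- *Part of the clean answer is already planned.* Before covariate adjustment, the logistic step's probability of densitometric osteoporosis given a fracture is the PPV against DXA. Table 8.1.2.1 also lists DXA and fracture diagnoses separately. This stands, but DXA-referenced sensitivity, specificity, NPV and likelihood ratios are still missing.
- *The acceptance share may be small.* Section 4 asks for a proven, non-pathological, minimal-trauma fracture. This stands: at q = 0.10, PPV rises by only 6 points. The plan fixes neither the share nor the read, so a large effect cannot be excluded.
- *Moving to DXA alone also changes the target condition.* It drops fractures proven from history, which are not incorporation. This stands too. As an illustration, suppose such fractures occur in 20% of DXA-negative, imaging-positive women. PPV without imaging-only diagnoses is (0.066 + 0.020)/0.166 = 52%. Accepting half of the remaining 0.080 gives (0.086 + 0.040)/0.166 = 76%. The shift is 24 points, not 30: smaller, but still large.
- *Clinically, the fracture is the disease.* Section 1.1 says that "a vertebral fracture is consistent with a diagnosis of osteoporosis" when no DXA result exists. That supports reporting how many diagnoses imaging adds. It does not support calling them evidence of accuracy.

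**Conclusion.** The point holds. As written, the 2x2 table has partial incorporation bias. With other qualifying fractures held fixed, counting imaging-only fractures raises PPV, specificity, sensitivity and LR+. The net difference from a DXA-only reference also depends on how many women qualify only through non-imaging fractures, which lower sensitivity, NPV and LR+. In the main illustration PPV runs from 40% to 100% and LR+ from 1.8 to infinity as q goes from 0 to 1. These sizes rest on assumed values for the odds ratio, DXA prevalence, q and r.

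Three stronger readings are not supported:

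- A reader might infer that every imaging fracture counts as osteoporosis, making PPV and specificity 100% by construction. Section 4's conditions on the fracture do not say so.
- A reader might infer that every measure must look better than against DXA, or that LR+ must exceed 1 without any association. The cases with r = 0.10 show otherwise.
- A reader might see a similar circularity in the risk-factor models of 8.1.2.2. The only reason given there for the BMD coding concerns the fracture model, so that text does not establish one.

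No primary or secondary estimate is affected. The change should be made, but it is confined to one exploratory table.

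**What to change.** In 8.1.3, or in the separate SAP promised in 8.1, make densitometric osteoporosis (T-score of -2.5 or lower at any of the three sites) the reference for sensitivity, specificity, PPV, NPV and likelihood ratios. This matches the logistic/ROC step.

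Report separately, labelled as descriptive yield and not accuracy, the number and share (95% CI) of women who meet the section 4 definition only through a vertebral fracture on study imaging, and state which read is used. The fragility-fracture row of Table 8.1.2.1 cannot supply this because it pools imaging with history. In the main illustration the count would be 2565×0.100×q, or about 64, 128 and 192 women at q = 0.25, 0.50 and 0.75 (8%, 15% and 22% of all women classed as osteoporotic).

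Optionally, add a sensitivity analysis whose reference is DXA osteoporosis or a fracture proven without study imaging. It stays closer to the study definition without using the index test.

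The cost is about two sentences and one table line, with no new data. The downside is less favourable accuracy figures, and women with fracture-only osteoporosis count as reference-negative in the main accuracy table. The yield line keeps those diagnosed only by study imaging visible, and the optional analysis restores those with fractures proven otherwise.

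### Exploratory objective 2 concerns vertebral imaging in local practice, but its analysis tests only the blinded expert reading, and no output addresses treatment

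*Combined protocol and SAP*

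**What the plan says.** Section 2.3 states the second exploratory objective: "To assess the diagnostic role of vertebral imaging for the screening of osteoporosis and pharmacological treatment in China's local clinical practice".

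Section 8.1.3 analyses it as a binary diagnostic test. The truth is the study's osteoporosis diagnosis, "whereas the blinded vertebral imaging outcome will be the diagnostic tool". The companion logistic and ROC analysis is meant to "assess the probability of a subject with adjudicated vertebral fracture will have densitometric osteoporosis", so it uses the adjudicated reading as well. The outputs are sensitivity, specificity, PPV, NPV, likelihood ratio and AUC.

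Section 4 (Vertebral Radiology) defines the reading: "Two (2) experienced radiologists who are blinded to the study will separately review the vertebral morphology". It adds that "Radiologists will receive additional training to reduce variability between inter-observer interpretations", and on disagreement "a third party radiological review will give a final decision". Section 6.1.2.3 repeats the two-plus-one arrangement.

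For the first exploratory objective, Section 8.1.3 treats the onsite reading as a separate test: "The diagnostic accuracy of onsite vertebral imaging will be tabulated by a simple 2*2 contingency table against blinded adjudication".

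**The concern.** The objective asks what imaging contributes where it is read locally. The analysis answers for a reading made by trained study experts with a tie-break. The plan regards onsite error as unknown and worth estimating, yet leaves it out of the one analysis where it would affect the screening conclusion. No section sets the onsite reading against osteoporosis, and none explains why the blinded reading was chosen for this objective.

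The treatment half of the objective has no output at all. Accuracy measures do not show how many women imaging would identify who are not already identified by T-score, known fracture or current therapy. Section 1.1 gives this as the motivation: most vertebral fractures go undiagnosed, and early diagnosis bears on later therapy.

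At stake is the interpretation of an exploratory result: expert-reader accuracy could be taken as support for local screening.

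**Working it through.** The plan states no accuracy figure for this analysis, so there is none to reproduce. The mismatch rests on the texts above. The arithmetic tests only its direction and plausible size.

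**Direction.** Let p1 and p0 be the proportions with an adjudicated fracture among women with and without osteoporosis (p1 > p0). Let se and sp be the onsite sensitivity and specificity against adjudication, with k = se + sp − 1 > 0. Assume onsite errors do not depend on osteoporosis status given the adjudicated result. Then:

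- onsite positive, osteoporosis: (1 − sp) + k·p1
- onsite positive, no osteoporosis: (1 − sp) + k·p0
- onsite Youden index: k·(p1 − p0), below the blinded p1 − p0 for any imperfect reader
- onsite LR+: [(1 − sp) + k·p1] / [(1 − sp) + k·p0], below p1/p0 whenever sp < 1; PPV falls with it
- onsite sensitivity exceeds p1 when (1 − p1)(1 − sp) > p1(1 − se), that is, when over-calling outweighs missed fractures

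**Size, illustration only.** Inputs:

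- Vertebral fracture prevalence 16.6%: Table 8.3.1 prevalences weighted by its group sizes, 85.98/518.
- Osteoporosis prevalence 27.3% (Section 1.1), taken here as the T-score prevalence.
- Assumption: 50% of adjudicated fracture cases have T-score ≤ −2.5 (range 40–60%).
- Assumption: onsite settings chosen so that overall agreement, 0.166·se + 0.834·sp, is about 92–94%. Section 4 cites that range for readers differing in experience and method; it does not describe these sites.

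Against T-score ≤ −2.5 alone, p1 = 0.166 × 0.5/0.273 = 0.304 and p0 = 0.166 × 0.5/0.727 = 0.114.

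| Reading (se/sp) | Sensitivity | Specificity | PPV | LR+ | Youden |
|---|---|---|---|---|---|
| Blinded | 30.4% | 88.6% | 50.0% | 2.66 | 0.190 |
| Onsite 60/98 | 19.6% | 91.4% | 46.1% | 2.28 | 0.110 |
| Onsite 75/96 | 25.6% | 87.9% | 44.2% | 2.11 | 0.135 |
| Onsite 90/94 | 31.5% | 84.4% | 43.2% | 2.02 | 0.159 |

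PPV, LR+ and Youden fall in every row. Sensitivity rises in the last row and specificity rises in the 60/98 row. The unadjusted AUC of a binary reading is (1 + Youden)/2, so at 75/96 it is 0.567 against 0.595. Over the 40–60% overlap range, Youden is 0.106–0.273 blinded and 0.075–0.194 for onsite 75/96.

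**The planned reference.** Section 4 defines osteoporosis as T-score ≤ −2.5 or a proven fragility fracture, and lets the study radiograph contribute to the fracture criterion; the footnote to Table 8.1.2.1 says the same. Suppose every adjudicated fracture counts and other fragility fractures are ignored. Composite prevalence is then 0.273 + 0.166 × 0.5 = 0.356, and blinded sensitivity is 0.166/0.356 = 46.6%. Blinded specificity and PPV are 100% by construction, because no fracture-positive woman can lack the diagnosis. Onsite 75/96 gives sensitivity 37.1%, specificity 96%, PPV 83.7% and Youden 0.331 against 0.466. At 90/90, onsite sensitivity is 47.3%, slightly above the blinded figure. Part of the gap under this reference is therefore the blinded reading being compared with itself.

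**The case against.** A two-step reading of the plan is defensible: first the value of correctly read imaging, then how well sites read it. Section 8.1.3 labels the test openly as blinded, and Section 8.2.1 gives blinded adjudication as a general protection against measurement bias. This supports keeping the blinded analysis. It does not supply the missing one, since onsite-versus-adjudicated accuracy converts to onsite-versus-osteoporosis accuracy only under the independence assumption, which the plan neither states nor tests.

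That assumption may fail. DXA and radiograph are normally done at the same visit, and blinding is specified only for the adjudicators. An onsite reader who knows the BMD or history might call more fractures in osteoporotic women, which would raise apparent onsite accuracy. This stands as a caveat on the direction.

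Table 8.1.2.1 already splits osteoporosis by DXA and by fragility fracture, which shows part of what fracture criteria add. It isolates neither imaging nor treatment status.

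A reader might infer that every planned accuracy figure is inflated, or that the figures will be presented as local-practice results. The documents support neither. Sensitivity can be higher onsite, and so can specificity against T-score; no section says how the results will be labelled. That local clinics lack an equivalent reading is likewise an inference, though the plan's own onsite/blinded contrast supports it.

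**Conclusion.** The point holds as a mismatch between objective and analysis. The blinded reading is the only test evaluated, the onsite reading is never set against osteoporosis, and the treatment part has no output.

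Lower onsite discrimination, PPV and LR+ follow algebraically, but only if onsite errors are independent of osteoporosis given adjudicated status and, for PPV and LR+, onsite specificity is below 100%. The size cannot be fixed from the documents. In the T-score illustration the Youden index falls from 0.190 to between 0.110 and 0.159, and PPV from 50% to between 43% and 46%; these figures rest on assumed onsite accuracy and 50% overlap.

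Replacing the index test alone would not be enough, because the composite reference can contain the study radiograph. The change is worth making before the separate SAP announced in Section 8.1 is finalised. It affects no primary or secondary estimate.

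**What to change.** In Section 8.1.3 and the separate SAP:

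1. Report sensitivity, specificity, PPV, NPV, likelihood ratio and AUC for the onsite reading, recorded before the adjudicated result is known, beside the same measures for the blinded reading. Label the onsite figures as the local-practice result and the blinded figures as the expert-reader result.
2. Show both readings against T-score ≤ −2.5 alone as well as against the composite diagnosis, and state that the composite can include the study radiograph.
3. Tabulate, with 95% CI, the number and percent of women with a vertebral fracture (onsite, then adjudicated) who have no T-score ≤ −2.5, no previously known fragility fracture and no current antiresorptive treatment. This counts the women identified by imaging alone; it implies no treatment rule.

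The inputs are already required: the onsite result (Section 8.1.3), and T-score, fracture history and antiresorptive use (Sections 4 and 6.1.2.1). The protocol does not say how the onsite reading is made or recorded, so the SAP must specify that. The cost is a few extra exploratory tables, probably less favourable accuracy figures, and a caveat that onsite readers are not stated to be blinded to DXA or history.
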